Email: [contact]

Sponsor Pharmacist

[name]

NHS Greater Glasgow and Clyde Research &

Development Dykebar Hospital [name]

[name]

[contact]

Email: [contact]

Version 6: 16th July 2021 Page 4 of 87

Clinical Trial Coordinator

[name]

Cancer Research UK Clinical Trials Unit

Level 0

Beatson West of Scotland Cancer Centre

[name] **[contact] **[contact]

Email: [contact]

Clinical Trial Monitor

[name]
Cancer Research UK Clinical Trials Unit
Administration Building Gartnavel Royal Hospital

[name] **[contact]

Email: [contact]

Funder Details

Cancer Research U.K.
[name]
Research Funding Manager
Angel Building
[name]
[name]

Email: [contact]

Co-Investigator

[name] Senior Lecturer in Cancer Epidemiology Centre for Public Health Queen's University Belfast [name]

[contact]

E-mail: [contact]

Pharmacovigilance Manager

[name]

Cancer Research UK Clinical Trials Unit Beatson West of Scotland Cancer Centre

[name] **[contact] **[contact]

Email: [contact]

Email: [contact]

Lead Clinical Research Nurse

[name] CRUK Senior Nurse NI Cancer Trials Network East Podium, C-Floor Belfast City Hospital [name]

[contact] **[contact].

Email: [contact]

Patient Public Involvement Contact

[name]

N. Ireland Cancer Research Consumers' Forum

c/o NI Cancer Trials Centre

Belfast City Hospital

[figure not shown]
[name]

[figure not shown]
Email: [contact]

Version 6: 16th July 2021 Page 5 of 87

Study Schema for the BALLAD UK trial

A trial to evaluate the potential Benefit of Adjuvant chemotherapy for small bowel ADenocarcinoma

For Group 1 and Group 2 the choice of fluoropyrimidine will be made prior to randomisation.

In addition for Group 1 the choice of whether Oxaliplatin will be given or not or whether this will be randomised will be made prior to randomisation

Trial Summary

Title:

BALLAD UK: A trial to evaluate the potential benefit of adjuvant chemotherapy for small bowel adenocarcinoma (IRCI-002). The UK component of the GLOBAL BALLAD pooled data analysis

Design:

An open-label, randomised, controlled, multi-centre, trial with disease free survival as the primary endpoint. Data from BALLAD UK will be pooled with data generated from a number of different, individual, parallel prospective studies addressing the same objectives with similar designs brought together under the framework of the International Rare Cancer Initiative. This worldwide data collaboration is referred to as GLOBAL BALLAD. This protocol is for BALLAD UK, which is the component of GLOBAL BALLAD led from the UK. Other countries contributing data to GLOBAL BALLAD will develop their own protocol and put in place their own sponsorship arrangements and be responsible for trial management and safety reporting for the trials they develop.

Objectives:

- 1. Assessment of the efficacy of observation versus 24 weeks of adjuvant post-operative chemotherapy in resected stage I-IV small bowel adenocarcinoma (SBA).
- 2. Assessment of the efficacy of 24 weeks of adjuvant post-operative fluoropyrimidine 'monotherapy' regimen versus fluoropyrimidine plus Oxaliplatin combination chemotherapy regimen in resected stage I-IV small bowel adenocarcinoma (SBA).

Endpoints:

Primary Endpoint

Disease free survival (defined as time from randomisation to recurrence, development of new primary or death from any cause).

Secondary Endpoints

Overall survival, cost-effectiveness, toxicity, clinico-pathological, epidemiological and molecular profiling of SBA.

Population:

Patients with SBA that has been potentially cured surgically.

Eligibility:

Inclusion Criteria

- 1. R0 resected stage I, II, III or IV SBA
- 2. No evidence of residual or metastatic disease at laparotomy or on CT/MRI imaging of chest, abdomen and pelvis.
- 3. Patients must be registered and randomised within 14 weeks of surgery and commence chemotherapy within 16 weeks of surgery
- 4. ECOG Performance Status of 0 or 1
- 5. Absolute neutrophil account $\geq 1.5 \times 10^9/I$

Version 6: 16th July 2021 Page 7 of 87

- 6. Platelet count $\geq 100 \times 10^9/l$
- 7. Haemoglobin ≥90 g/l (previous transfusion is allowed)
- 8. AST and ALT \leq 2.5 x upper limit of normal (ULN). (At least one of ALT or AST MUST be performed)
- Creatinine clearance > 50 ml/min (calculated by Cockcroft Gault or Wright equation) or measured by EDTA
- 10. Serum bilirubin ≤ 1.5 x ULN
- 11. Signed and dated informed consent indicating that the patient has been informed of all the pertinent aspects of the trial prior to enrolment.
- 12. Age \geq 16 years
- 13. Willingness and ability to comply with scheduled visits, treatment plans and laboratory tests and other trial procedures.

Exclusion Criteria

- Non-adenocarcinoma histology of small bowel tumour which includes but is not confined to lymphoma, GIST, carcinoid or other neuroendocrine tumour, squamous carcinoma, melanoma or sarcoma.
- 2. Adenocarcinoma arising in the appendix or colorectum
- 3. Previous neo-adjuvant chemo(radio)therapy for SBA
- 4. Clinically significant cardiovascular disease (i.e. active or < 12 months since cerebrovascular accident, myocardial infarction, unstable angina, New York Heart Association [NYHA] grade II or greater congestive heart failure, serious cardiac arrhythmia requiring medication, uncontrolled hypertension)

- 5. Pregnancy/lactation or of child bearing potential and not using medically approved contraception. (Postmenopausal women must have been amenorrhoeic for at least 12 months to be considered of non-childbearing potential)
- 6. Previous invasive or non-invasive malignancy except:
 - (i) Ductal Carcinoma In Situ (DCIS) of the breast where treatment consisted of resection alone, (ii) Cervical carcinoma in situ where treatment consisted of resection alone, (iii) Basal cell or squamous cell carcinoma where treatment consisted of resection alone or radiotherapy, (iv) Superficial bladder carcinoma where treatment consisted of resection alone or with a single installation of intravesical chemotherapy or with BCG treatment, (v) Other cancers where the patient has been disease-free for at least 3 years and treatment was with curative

intent, and (vi) Other cancers with very low potential for recurrence can be discussed with the CI or his approved representative through the Glasgow CRUK Clinical Trials Unit where eligibility will be considered on an individual basis.

- 7. Complete dihydropyrimidine dehydrogenase (DPD) deficiency. Patients with partial DPD deficiency (characterised by certain heterozygous DPYD variants) may still be eligible for study treatment with fluorouracil or oral capecitabine with reduced starting doses based on the latest guidance available (see Section 5.1).
- 8. Known untreated coeliac disease (may be enrolled if diet controlled), untreated chronic inflammatory bowel disease or other cause of malabsorption or intestinal obstruction
- 9. Grade ≥ 2 peripheral neuropathy
- 10. Administration of any investigational drug within 28 days or 5 half-lives, whichever is longer, prior to receiving the first dose of trial treatment.
- 11. Previous hypersensitivity to platinum salts
- 12. Patients with clinically significant, active infections, or any other serious medical condition in which chemotherapy is contraindicated will be excluded
- 13. Patients with untreated vitamin B12 deficiency are excluded from receiving folinic acid as part of their chemotherapy regimen. However, these patients may be eligible for treatment with capecitabine fluoropyrimidine therapy, where no folinic acid is administered as part of the treatment regimen
- 14. Patients with clinically significant sensorineural hearing impairment are excluded from receiving oxaliplatin but will be eligible for the fluoropyrimidine monotherapy provided as a clinician's choice for patients in group 1 randomised to either observation or chemotherapy
- 15. Any patient receiving treatment with brivudine, sorivudine and analogues within 4 weeks prior to receiving the first dose of trial capecitabine or 5-FU.

Treatment:

Group 1 patients, where there is uncertain value of adjuvant chemotherapy, will be randomised to observation versus chemotherapy. The chemotherapy will be 24 weeks fluoropyrimidine

Version 6: 16th July 2021 Page 9 of 87

with or without Oxaliplatin or these patients can be randomised to receive Oxaliplatin or not as per Group 2 patients below. The choice of chemotherapy must be specified prior to randomisation.

Group 2 patients, where there is certain value of adjuvant chemotherapy, will be randomised to receive 24 weeks fluoropyrimidine chemotherapy either with or without Oxaliplatin. The choice of fluoropyrimidine must be specified prior to randomisation.

Duration:

Patients will be recruited into the trial over a period of 5 years and have a period of follow-up for up to 7 years.

Schedule of Assessments – Patients randomised to Observation Only

	!	Screening		Follow Up											
Trial Procedures	≤28 days prior to Reg/Rand	≤7 days prior to Reg/Rand	Reg/Rand	Month 3 Post Randomisation	Month 6 post randomisation	Month 9 post reg/rand	Month 12 post reg/rand	Month 18 post reg/rand	Month 24 post reg/rand	Month 30 post reg/rand	Month 36 post reg/rand	Annually until 7 yrs post reg/rand			
Informed Consent (1)	✓														
Review of Eligibility Criteria		√													
Medical History		✓													
Physical/Clinical Assessment (inc height and weight, BP, Pulse, assessment of neuropathy and assessment of sensorineural hearing impairment)		√		√	√										
Body Surface Area		✓													
ECG ⁽²⁾		√													
ECOG Performance Status		√													
Surgery ⁽³⁾	To be within 14 weeks of randomisation														
Laboratory Procedures		(/5)	T	1		T .	1	1	1						
Haematology (Co-ag) (4)		√ (5)													
Haematology (FBC)		√ (5)		√ (5)	√ (5)	√ (5)	√ (5)	√ (5)	√ (5)	√ (5)	√ (5)	√ (5)			
Urea & Electrolytes		√ (5)		√ (5)	√ (5)	√ (5)	√ (5)	√ (5)	√ (5)	√ (5)	√ (5)	√ (5)			
Liver Function Tests (7)		√ (5)		√ (5)	√ (5)	√ (5)	√ (5)	√ (5)	√ (5)	√ (5)	√ (5)	√ (5)			
Magnesium and estimated GFR		√ (5)													
Urine Pregnancy Test		✓													
Radiological Assessment															
CT Scan (chest, abdomen and pelvis) (8)	To be within 12 w entry						√ (9)		√ (9)		√ (9)				
Patient Questionnaires									•						
EORTC QLQ-C30 & CR29 QoL		√		√ (10)	✓	√ (10)	√	√	√						
EQ-5D		✓		√ (10)	✓	√ (10)	✓	✓	✓	✓	✓	✓			
Translational Research															
Tissue collection (11)	✓														
Blood Sample collection (12)		√													
DPD Deficiency Testing ⁽¹⁴⁾	✓														

Version 6: 16th July 2021

Schedule of Assessments – For patients randomised to 5-FU/FA +/- Oxaliplatin

	Scree	ening							Treatm	ent Cycl	е							Foll	ow Up			
Trial Procedures	≤28 days prior to Reg/Rand	≤7 days prior to Reg/Rand	Reg/Rand	Cycle 1	Cycle 2	Cycle 3	Cycle 4	Cycle 5	Cycle 6	Cycle 7	Cycle 8	Cycle 9	Cycle 10	Cycle 11	Cycle 12	Moth 9 post reg/rand	Moth 12 post reg/rand	Moth 18 post reg/rand	Moth 24 post reg/rand	Month 30 post reg/rando	Moth 36 post	Annually until 7 yrs post
Informed Consent (1)	_																					
Review of Eligibility Criteria		√																				
Medical History		· ✓																				
Physical/Clinical Assessment (inc height and weight, BP pulse, assessment of neuropathy and assessment of sensorineural hearing impairment)		√		√	*	~	*	√	√	√	~	√	*	√	*							
Body Surface Area		✓																				
ECG ⁽²⁾		√																				
ECOG Performance Status		✓		√	✓	√	√	√	√	√	√	√	✓	√	√							
Toxicity Assessment				✓	✓	✓	✓	✓	✓	✓	✓	✓	✓	✓	✓							
Administration of IMP ⁽¹³⁾				✓	✓	✓	✓	✓	✓	✓	✓	✓	✓	✓	✓							
Surgery ⁽³⁾	weeks o	vithin 16 of cycle 1 ate																				
Laboratory Procedures																						
Haematology (Clotting ⁽⁴⁾)		√ (5)		√ (6)	√ (6	√ (6)	√ (6)	√ (6)														
Haematology (FBC)		√ (5)		√ (6)	√ (6	√ (6)	√ (6)	√ (6)	√ (6)	√ (6)	√ (6)	√ (6)	√ (6)	√ (6)	√ (6)							
Urea & Electrolytes		√ (5)		√ (6)	√ (6	√ (6)	√ (6)	√ (6)	√ (6)	√ (6)	√ (6)	√ (6)	√ (6)	√ (6)	√ (6)							
Liver Function Tests (7)		√ (5)		√ (6)	✓	√ (6)	√ (6)	√ (6)	√ (6)	√ (6)	√ (6)	√ (6)	√ (6)	√ (6)	√ (6)							
Magnesium and GFR		√ (5)		√ (6)	√ (6	√ (6)	√ (6)	√ (6)														
Urine Pregnancy Test		√ (5)																				
Radiological Assessment																						
CT Scan (chest, abdomen and pelvis) (8)	To be 12weeks	within pre-trial															√ (9)		√ (9)		√ (9)	
Patient Questionnaires																						
EORTC QLQ-C30 & CR29 QoL		✓							✓						✓	✓	✓	✓	✓			
EQ-5D		✓							✓						✓	✓	✓	✓	✓	✓	✓	✓
Translational Research																						
Tissue collection (11)	✓																					
Blood Sample collection (12)		✓																				
DPD Deficiency Testing ⁽¹⁴⁾	✓																					

Version 6: 16th July 2021

Schedule of Assessments – For patient randomised to Capecitabine +/- Oxaliplatin

	Screening			Treatment Cycle								Follow Up							
Trial Procedures	<pre>≤28 days prior to Reg/Rand</pre>	≤7 days prior to Reg/Rand	Reg/Rand	Cycle 1	Cycle 2	Cycle 3	Cycle 4	Cycle 5	Cycle 6	Cycle 7	Cycle 8	Moth 9 post reg/rand	Moth 12 post reg/rand	Moth 18 post reg/rand	Moth 24 post reg/rand	Moth 30 post reg/rand	Moth 36 post reg/rand	Annually until 7 yrs post reg/rand	
Informed Consent (1)	✓																		
Review of Eligibility Criteria		✓																	
Medical History		✓																	
Physical/Clinical Assessment (inc height and weight BP, pulse, assessment of neuropathy and assessment of sensorineural hearing impairment)		~		√	~	~	√	~	~	✓	✓								
Body Surface Area		✓																	
ECG ⁽²⁾		✓																	
ECOG Performance Status		✓		√	✓	√	√	√	√	√	√								
Toxicity Assessment				✓	✓	✓	✓	✓	✓	✓	✓								
Administration of IMP ⁽¹³⁾				✓	✓	✓	✓	✓	✓	✓	✓								
Surgery ⁽³⁾	To be with weeks of c date	ycle 1																	
Laboratory Procedures		((5)		(15)	((6)	((6)	((5)	(15)	((6)	((5)	((5)								
Haematology (Clotting ⁽⁴⁾)		√ (5)		√ (6)	√ (6)	√ (6)	√ (6)	√ (6)	√ (6)	√ (6)	√ (6)								
Haematology (FBC)		√ (5)		√ (6)	√ (6)	√ (6)	√ (6)	√ (6)	√ (6)	√ (6)	√ (6)	√ (6)	√ (6)	√ (6)	√ (6)	√ (6)	√ (6)	√ (6)	
Urea & Electrolytes		√ (5)		√ (6)	√ (6)	√ (6)	√ (6)	√ 6)	√ (6)	√ (6)	√ (6)	√ (6)	√ (6)	√ (6)	√ (6)	√ (6)	√ (6)	√ (6)	
Liver Function Tests (7)		√ (5)		√ (6)	√ (6)	√ (6)	√ (6)	√ (6)	√ (6)	√ (6)	√ (6)	√ (6)	√ (6)	√ (6)	√ (6)	√ (6)	√ (6)	√ (6)	
Magnesium and GFR		√ (5)		√ (6)	√ (6)	√ (6)	√ (6)	√ (6)	√ (6)	√ (6)	√ (6)								
Urine Pregnancy Test		√ (5)																	
Radiological Assessment																			
CT Scan (chest, abdomen and pelvis) (8)	To be with weeks pre entry	e-trial											√ (9)		√ (9)		√ (9)		
Patient Questionnaires									,										
EORTC QLQ-C30 & CR29 QoL		✓					✓				✓	✓	√	✓	√				
EQ-5D		✓					✓				✓	✓	✓	✓	✓	✓	✓	✓	
Translational Research																			
Tissue collection (11)	✓																		
Blood Sample collection (12)		✓																	
DPD Deficiency Test ⁽¹⁴⁾	✓										 								

Version 6: 16th July 2021

- All patients must be consented to the trial prior to randomisation and prior to any treatment starting.
- A baseline ECG should be performed within 7 days of randomisation, however ECGs performed up to 20 days prior to randomisation will be accepted.
- (2) (3) Patients should be randomised within 14 weeks of surgery and treatment should start within 2 weeks of randomisation date. However as long as the surgery to cycle 1 treatment start date is ≤ 16 weeks the patient will be considered eligible. Please contact your co-ordinating trials office for clarification.
- Coagulation tests only required to be performed in patients on treatment with anti-coagulants after baseline.
- (5) Pre-randomisation and C1 bloods should preferably be taken within 7 days prior to randomisation/C1 date, but bloods taken up to a maximum of 9 days pre-randomisation/C1 date will be accepted
- (6) From cycle 2 onwards, pre-cycle bloods should be performed within 2 days of day 1 of a treatment cycle. Bloods taken for a follow-up visit may be completed within one month prior to the scheduled visit. Once the primary endpoint of disease free survival has been reached FBC and biochemistry tests are no longer required. Pre
 - cycle (excluding pre-randomisation) blood tests may be completed locally / at a patient's GP. The blood test results must be signed dated and filed in patient notes for source verification.
- At least one of AST or ALT must be performed to assess liver function.
- (8) CT scan is the preferred method of radiological assessment, however it is acceptable to use MRI of abdomen and pelvis and chest CT. The baseline CT scan should be
 - performed within 12 weeks of the date of randomisation. Additional CT scans can be performed at any stage during the trial if clinically indicated
- CT Scans performed up to 42 days prior to the scheduled follow up visit date will be accepted and used for that follow up visit.
- (10)Quality of life assessments at 3 and 9 months should be posted to patient's home for completion for patients randomised to observation only
- For those patients who have consented to tumour sample collection, paraffin embedded tumour tissue obtained at surgical resection of the primary tumour prior to entry to BALLAD UK should be collected. (11)Further instructions will be available in a separate translational research manual
- For those patients who have consented to blood sample collection. Bloods should be collected prior to the start of therapy. Further instructions will be available in a separate translational research manual (12)
- (13)All drugs administered as part of the Group 1 & 2 randomisations are considered Investigational Medicinal Products (IMPs) for the purposes of this protocol.
- Should be performed at any time prior to randomisation if standard of care or clinically indicated (14)

Version 6: 16th July 2021 Page 14 of 87

1	INTRODUCTION

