4 TRIAL DESIGN

4.1 Trial Schedule

For Group 1 patients randomised to observation only:

Clinic visits are mandated at screening, 3 months post randomisation, 6 months post randomisation, 9 months post randomisation, 12 months post randomisation then every 6 months until 3 years post randomisation and then annually for up to 7 years post randomisation.

For Group 1 patients randomised to chemotherapy and for all Group 2 patients:

Clinic visits are mandated at screening, during treatment for chemotherapy, 9 months post randomisation, 12 months post randomisation then every 6 months until 3 years post randomisation, then annually for up to 7 years post randomisation.

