4.1.2 Evaluations While on Trial Treatment

Prior to each cycle of chemotherapy the following tests should be performed:

- ECOG performance status
- Toxicity Assessment (only toxicities which are grade 2 or above require entry to the CRF)
- If the patient has been randomised to receive oxaliplatin treatment clinical assessment of neuropathy should be performed at all study visits
- If the patient has been randomised to receive oxaliplatin treatment clinical assessment of sensorineural hearing impairment should be performed at all study visits
- Haematology blood sample (full blood count). From cycle 2 onwards pre-cycle bloods should be performed within 2 days of treatment. For patients on anti-coagulant therapy, appropriate clotting factors should be tested at each chemotherapy visit.
- Biochemistry including U&E, LFT, magnesium and calculated or measured GFR. From cycle 2 onwards pre-cycle biochemistry should be performed within 2 days of treatment
- QoL questionnaires when required EQ-5D and EORTC QLQ-C30 and CR29 (at 3 and 6 months post randomisation)

If a patient stops their allocated treatment early or if the patient experiences treatment delays the BALLAD UK follow-up visits will still be due as per the protocol schedule i.e. timed relative to date of randomisation. This is the required procedure even if the patient has experienced treatment delays and is still receiving chemotherapy treatment.

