4.1.4 Follow up Evaluations

Patients will be followed up 9 months post randomisation and 12 months post randomisation. After that they will have visits on a six monthly basis until 3 years post randomisation and will then have

annual visits for up to 7 years post randomisation.

Follow-up CT Scanning

CT Chest Abdomen and Pelvis will be performed at approximately 12, 24 and 36 months post randomisation. (Contrast enhanced CT Chest, abdomen and pelvis is the preferred method of assessment but MRI abdomen and pelvis with non-contrast enhanced chest CT may be used instead

where clinically indicated).

Additional CT scans may also be conducted as clinically indicated based on symptoms, clinical markers

or to accommodate sites usual scanning regimen.

CT scans performed within 42 days of the follow-up visits may be used for disease assessment. If the

time interval from CT to follow up visit is more than 42 days a new CT scan should be performed.

If a patient has reached the primary endpoint of the trial and has a recurrence or a new primary tumour

(CT confirmed) then further protocol mandated CT scans are no longer required. Any post recurrence

CT scans should be performed as per local practice at the discretion of the investigator. The results of any further scans should be recorded in the appropriate section of the Case Report Form (CRF) unless

the patient has commenced further palliative systemic therapy.

Follow-up Quality of Life Assessments

Please see the schedule of assessment for collection time-points during treatment (baseline, 3 and 6

months post randomisation).

EORTC QLQ-C30 and CR29 will be completed at 9, 12, 18 and 24 months post randomisation for all

arms of the trial.

The EQ-5D will be completed at 9, 12, 18, 24, 30, 36, 48, 60 72 and 84 months post randomisation

for all arms of the trial.

For patients that have a recurrence or have a new primary tumour the quality of life questionnaires

should continue to be completed as per schedule of assessments provided it is deemed appropriate to

ask the patient to do so.

Resource use for health economic assessment

Version 6: 16th July 2021 Page 33 of 87

Resource use data collection for the health economic assessment will be limited to health service resource use in the secondary care setting. Data (hospital inpatient, outpatient and day cases, cytotoxic drug use at relapse) will be collected on the treatment and follow-up forms.

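### The quality-of-life forms are posted home in the observation arm only, and the two on-treatment forms follow cycles in the tables but months in the text: an avoidable risk of bias in the adjuvant QoL and QALY comparison

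*Protocol*

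**What the plan says.** **Mode.** In the observation table, the rows for QLQ-C30/CR29 and for EQ-5D both carry footnote (10) at months 3 and 9: "Quality of life assessments at 3 and 9 months should be posted to" the home, for observation patients only. The two chemotherapy tables carry no such footnote. Section 4.1 says of the observation arm: "Clinic visits are mandated at screening, 3 months post randomisation, 6 months post randomisation, 9 months post randomisation, 12 months post randomisation". Section 4.1.3 lists QoL among the items done at the 3- and 6-month visits.

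**Timing.** Section 4.1.2, in its list of what is done before each chemotherapy cycle, has: "QoL questionnaires when required EQ-5D and EORTC QLQ-C30 and CR29 (at 3 and 6 months post randomisation". Section 4.1.4 gives the same months and refers to the tables: "Please see the schedule of assessment for collection time-points during treatment (baseline, 3 and 6" months. In the tables, the row "EORTC QLQ-C30 & CR29 QoL" is ticked at cycles 6 and 12 for 5-FU and at cycles 4 and 8 for capecitabine. For observation it is ticked at months 3 and 6. The EQ-5D row has the same on-treatment ticks. From month 9 the arms share one calendar: "EORTC QLQ-C30 and CR29 will be completed at 9, 12, 18 and 24 months post randomisation for all" arms.

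**Use.** Section 7.3.4 analyses QoL by AUC techniques. Section 7.3.5 builds QALYs from EQ-5D, also as an area under the curve, for both trial questions.

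**The concern.** For the adjuvant question, two features of collection differ by randomised arm in an open-label trial. The first is where and how the month 3 and month 9 forms reach the patient. The second is the clock that sets the first two post-baseline forms. Place of completion can affect both the answers and the chance that a form comes back. A cycle-based column can also lose forms selectively: a patient who stops before cycle 8 or 12 has no column for the second form, and this can happen only under chemotherapy. An analysis can use actual completion dates, but it cannot undo a difference in mode or recover forms that were never given out.

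There is also a practical fault. A site cannot follow footnote (10) and section 4.1.3 together at month 3, and the text and the tables give different answers on when the chemotherapy forms are due.

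**Working it through.** **1. Mode, passages side by side**

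| Time point | Observation | Chemotherapy |
|---|---|---|
| Month 3 | Clinic visit mandated (4.1); QoL listed at it (4.1.3); form posted home (footnote 10) | Ticked at a treatment cycle; no posting instruction |
| Month 6 | Clinic visit mandated; form ticked, no footnote | Ticked at the last cycle; no month-6 visit in 4.1 or the tables |
| Month 9 | Clinic visit mandated; form posted home (footnote 10) | Clinic visit mandated; no posting instruction |

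The protocol gives no reason for posting.

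**2. Timing**

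Inputs: cycle length 2 weeks for 5-FU and 3 weeks for capecitabine (examples in 5.3.1 and 5.3.2); lag from randomisation to cycle 1 of 0-2 weeks (footnote 3); form completed before the cycle (4.1.2). One month is 365.25/12/7 = 4.35 weeks, so months 3, 6 and 9 are weeks 13.0, 26.1 and 39.1.

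Week of form = lag + (cycle − 1) × cycle length.

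| Form | Calculation | Weeks, lag 0-2 | Early by |
|---|---|---|---|
| 5-FU, cycle 6 | 5 × 2 = 10 | 10-12 | 1-3 weeks |
| Capecitabine, cycle 4 | 3 × 3 = 9 | 9-11 | 2-4 weeks |
| 5-FU, cycle 12 | 11 × 2 = 22 | 22-24 | 2-4 weeks |
| Capecitabine, cycle 8 | 7 × 3 = 21 | 21-23 | 3-5 weeks |

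A cumulative delay of 3-4 weeks moves the forms to weeks 12-16 and 24-28. With no delay, the interval from the second on-treatment form to month 9 is 39 − 24 = 15 to 39 − 21 = 18 weeks.

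**3. What timing alone does to the AUC (illustration)**

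The protocol gives no QoL values. Assumed: a treatment dip of 5-20 points on a 0-100 scale, full from week 6 to week 26, recovered by month 9. The trapezoid rule is applied over 24 months.

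- Forms at weeks 13.0 and 26.1: mean AUC change −1.25 (dip 5) and −4.98 (dip 20).
- Undelayed forms at their actual dates: −1.22 and −4.90, a difference of 0.03-0.08 points. If nominal dates are used, the difference is at most about 0.02.
- Forms at weeks 16 and 28: a difference of 0.10-0.42 points.

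The assumed path is flat within cycles, so it says nothing about any swing within a cycle.

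**4. What mode could do**

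Suppose posting shifts the observation score by d points at months 3 and 9. Each of those forms has neighbours 3 months away on both sides, so its trapezoid weight is (3 + 3)/2 = 3 months. The 24-month mean AUC moves by (3 + 3)/24 × d = 0.25d. Assumed values d = 1, 3 and 5 give 0.25, 0.75 and 1.25 points. The documents give neither a size nor a sign for d.

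**The case against.** Several stronger readings are tempting, and the documents do not support them.

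- *The AUC comparison is biased.* That is not shown. The instruments are self-completed in every arm, so what differs is delivery and place, not self-report against interview. No mode effect or differential missingness is documented, and the timing effect in the illustration is small.
- *Footnote (10) contradicts the 3- and 6-month schedule.* It does not. Months 3 and 9 are both scheduled QoL times. The timing mismatch lies between the cycle columns and sections 4.1.2 and 4.1.4.
- *Dose delays make the drift worse.* Undelayed forms are early, so ordinary delays first bring them closer to weeks 13 and 26. Only longer ones overshoot.
- *All forms can simply be moved to clinic without cost.* This fails at month 6, where chemotherapy patients have no visit.

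It can also be said that the cycle columns are meant as approximations to 3 and 6 months. If the form were completed at the end of the ticked cycle rather than before it, it would fall at weeks 12-14 and 24-26, close to nominal. Section 4.1.4 also sends the reader to the tables. That is fair, but section 4.1.2 lists the form with the pre-cycle tests, and neither reading helps a patient who stops early. Section 4.1.2 keeps follow-up visits on the randomisation clock after early stopping; the on-treatment QoL columns have no such rule. The use of actual or nominal dates can be left to the statistical analysis plan and is no fault here.

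What stands is the conflict over posting, the conflict between cycle and calendar, and the fact that both fall along the line of randomisation.

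**Conclusion.** There are two genuine inconsistencies, and together they create an avoidable risk of bias in the QoL AUC and QALY comparison for the adjuvant question. Its size and direction are unknown. The timing gap is 1-4 weeks at month 3 and 2-5 weeks at month 6, assuming pre-cycle completion, no delay and 0-2 weeks to cycle 1. Under the assumed dips this is worth less than 0.1 point of mean AUC, and up to about 0.4 if the forms slip to weeks 16 and 28. The posting difference would carry a quarter of any mode effect into the 24-month mean.

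The scope is limited. These are secondary endpoints, and the time points from month 9 to month 24 are common to all arms, although the mode still differs at month 9. The oxaliplatin question is essentially unaffected: both its arms share one schedule and mode within the chosen fluoropyrimidine, which is a stratification factor, apart from any difference in delays or early stopping. The change is worth making because it is cheap, not because the comparison is shown to be wrong.

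**What to change.** 1. Delete footnote (10). Give the month 3 and month 9 QLQ-C30/CR29 and EQ-5D forms at the observation visits that section 4.1 already mandates, with post only as back-up for a missed visit, in any arm.
2. State in the tables and in sections 4.1.2 and 4.1.4 that time from randomisation governs the two on-treatment forms in every arm, including for patients who stop treatment early.
3. Month 3: use the treatment visit nearest week 13. With undelayed 2- or 3-weekly visits, the nearest is at most half a cycle away (1 or 1.5 weeks).
4. Month 6: collect at about week 26 by one common mode in all arms, for example the same take-home or postal form for everyone. Chemotherapy patients have no visit then, so a clinic form for observation and a postal form for chemotherapy would recreate the asymmetry.
5. While editing, correct the pointer in section 4.3.2, which sends QoL timing to a section 4.1.5 that does not exist.

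The cost is mainly wording, with no added visits. Some forms will not coincide with a cycle day, and the month-6 form in the chemotherapy arms may have to be completed away from clinic. With a common take-home or postal form, the same would apply to observation patients.
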